	
Contact Person: [name] [contact] Date Prepared: April 2, 2002
 
2. Device Name Proprietary Name: 300 PV Complete Electrotherapy System Common/Usual Name: Electrical Muscle and Nerve Stimulator Classification Names: Powered Muscle Stimulator, Transcutaneous Nerve Stimulator, interferential Current Stimulator, External Neuromuscular Functional Stimulator
 
3. TENS Parameters: Active and Placebo Units
 
 • TENS Frequency – 10 to 100 Hz, SMP mode • TENS Pulse Width - 200 µs • TENS Intensity - Maximal tolerable intensity • Duration: 2 h per day during activity. The 2 h may be broken into smaller segments of time with a minimum of 30 minutes. • Administration - Daily • TENS Location: TENS electrode on the skin will be a 4 x 7 butterfly electrode to the cervical and lumbar region. • Placebo TENS Unit - The placebo TENS unit will deliver current for 45s ramping to 0 in the last 15s.

Study Summary
	
This is a phase II randomized, double-blind, placebo controlled multi-center clinical trial involving a device, TENS, to assess the efficacy of TENS on pain with movement over a 1 month period in subjects with fibromyalgia. After participating in the 1 month random assignment, all subjects will receive active TENS for 1 month. Subjects will receive a phone call weekly from the study coordinator regarding progress.
 
 • Screening: Telephone screen for eligibility for the study • Assessor – performs baseline and all testing except TENS allocation and TENS home instruction. The assessor is blinded to TENS treatment. • TENS Allocator – performs TENS allocation, home instructions and questions regarding TENS

Demographic and Outcome Measures
	
 • Consent • Health History/Demographic • Vital Signs • Confirmation of ACR 1990 Criteria for FM/Tender Point Exam • 2010 ACR Criteria • NRS Rest Pain, Rest Fatigue, Movement Pain, Movement Fatigue • BPI • PROMIS • FIQR • SF-36 • MAF • TSK • IPAQ • PSQI • PSEQ • PCS

	
 • Global Impression of Change • Accelerometry (Actigraph) • 6MWT • STS • FR • PPT • CPM • TENS

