Aim #4: The primary endpoints of Aim #4 are the FIQR and SF-36 prior to randomization. PROMIS modules (also obtained prior to randomization) for depression, fatigue, pain behavior, pain interference, physical function, satisfaction with social roles, and satisfaction with discretionary social activities will be summarized and compared to validated FM instruments (FIQR and SF-36). Scores from each of the PROMIS modules will be compared to corresponding FIQR and SF-36 domains (see Table 1) by estimating Pearson correlation coefficients and testing for nonzero correlation. Multiple linear regression may also be used to investigate this relationship while controlling for potential confounding variables. Finally, FIQR, PROMIS, and SF-36 will be obtained at four different time points during this study (pre-treatment, randomized phase, and non-randomized active TENS). Summaries will include values at pre-treatment, changes from pre-treatment and percent changes. In addition to changes observed in the randomized phase, linear mixed models may also be utilized where treatment status (pre-treatment, randomized treatment, and non-randomized active TENS) is treated as a time-varying covariate to estimate the impact of changes in treatment status on these outcomes.

As an exploratory analysis, further investigation of changes in pain, responder

	status, and relationships between endpoints will be conducted for data collected during the non-randomized phase and will include those with an additional month of active TENS (originally randomized to active TENS) as well as those with a single month of active TENS (originally randomized to placebo TENS and no treatment control). Finally, exploratory examinations of the relationships between changes in pain, sensory, and quality of life measures may utilize multivariate methods (e.g. partial least squares and principal component analysis) and classification and regression trees.
Safety Measures	Physical Exam Vital Signs Clinical signs and symptoms Adverse Event analysis Increased pain with testing follow-up: Participants who experience an increase in testing will be contacted the day after testing about the status of the increase in pain (Added 12/2014) Safety analysis

Schedule of Visits and Evaluations.

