	FTSTS	V2 V3 V4	Function; Measure of leg strength	ICC 1 >0.95	r=0.59-0.88 LBP r=0.46-0.76 Control	^{65, 66}

	FR	V2 V3 V4	Function; Measure of balance	r=0.95	r=0.7	^{27, 67}
	Actigraph: Actisleep+	Week Before V2 V3 V4	Function: Activity and Sleep Accelerometer worn on wrist	NA	NA	NA
Quantitative Sensory Testing	PPT	V2 V3 V4	Deep mechanical hyperalgesia; Pressure Pain Thresholds	r=0.79-0.94 ICC = 0.85- 0.99 Test- retest=0.70 -0.94	Significant differences between healthy and RA subjects (p<0.05)	⁶⁸⁻⁷²
	CPM (DNIC)	V2 V3 V4	Central Inhibition	Face validity as the same test in animals activates descending inhibitory pathways		

*Table 3:
List of
equipment,
form per
test and
measure*

Order of Testing FAST June 2014

Order of Testing FAST June 2014							
Key:							
Blue= Assessor	Black= Subject	Red= TENS Allocator					
Session 1	Session 2		Session 3		Session 4		
Pre-consent Eligibility Screen	NRS Rest - Pain,Fatigue		NRS Rest - Pain,Fatigue		NRS Rest - Pain,Fatigue		
Reimbursement Form	FIQR		FIQR		FIQR		
Consent	Medication Log		Medication Log		Medication Log		
Confirmation of Consent	Eligibility		Adverse Event Screen		Adverse Event Screen		
Adverse Event Screen	Adverse Event Screen	Download Actigraph Data	Questionnaires (4-5) 1990 & 2010 ACR	Download Actigraph Data	Questionnaires (4-5) 1990 & 2010 ACR	Download Actigraph Data	
Medication Log	Questionnaires (4-5)		6MWT	Download/Record TENS Data	6MWT	Download/Record TENS Data	
Health History	6MWT		FTSTS		FTSTS		
NRS Rest - Pain,Fatigue	FTSTS		FR		FR		
FIQR	FR		PPT		PPT		
Height, Weight	PPT		TENS Treatment 1	5 min TENS Check	TENS	5 min TENS Check	
1990 FM ACR	TENS	5 min TENS Check	Questionnaires during TENS(4-5)		Questionnaires during TENS(4-5)		
2010 FM ACR	Questionnaires during TENS(4-5)		NRS Rest - Pain,Fatigue		NRS Rest - Pain,Fatigue		
Eligibility/Review	NRS Rest - Pain,Fatigue		PPT		PPT		
TENS Tolerance Test	PPT		6MWT (NRS Mvmt Pain, Fatigue, BORG)		6MWT (NRS Mvmt Pain, Fatigue, BORG)		
Actigraph	6MWT (NRS Mvmt Pain, Fatigue, BORG)		FTSTS (NRS Mvmt Pain, Fatigue)		FTSTS (NRS Mvmt Pain, Fatigue)		
Adverse Event Screen	FTSTS (NRS Mvmt Pain, Fatigue)		FR		FR		
Blood Draw	FR		CPM		CPM		
	CPM		Blinding question		GIC	TENS off	
	TENS Home		Turn off TENS		Survey		
	Actigraph Home		GIC		Survey		
	AES		Blinding question				
	Record and Clear Data		Debriefing (Active may be done)				
			Record/Clear Data				
			TENS Treatment 2	5 min TENS Check			
			NRS Rest - Pain,Fatigue				
			PPT				

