			6MWT (NRS Mvmt Pain, Fatigue, BORG)				
			FTSTS (NRS Mvmt Pain, Fatigue)				
			FR				
			CPM				
			TENS Home				
			Actigraph Home				
			AES				
			Record and Clear Data				

Table 3: List of equipment, form per test and measure

Area	Form	Visit	Equipment: Clipboards, Pens, Computer/Form
	Screening Log	Pre Visit	Computer/Form
Surveys	Consent	1	Computer/Form
	Health History/Demographic	1	Computer/Form
	Diagnostic Confirmation	1	Computer/Form
	Eligibility Confirmation	1, 2	Computer/Form
	FIQR	1,2,3,4	Computer/Form
	MAF	2,3,4	Computer/Form
	TSK	2,3,4	Computer/Form
	Medication	1,2,3,4	Computer/Form
	SF-36	2,3,4	Computer/Form
	PROMIS	2,3,4	Computer/Form
	IPAQ	2	Computer/Form
	PSQLI	2	Computer/Form
	PSEQ	2	Computer/Form
	PCS	2	Computer/Form
	Blinding Question Researcher and Subject	3	Computer/Form
	Global Impression of Change	3, 4	Computer/Form
Pain	NRS	1,2,3,4 Previsit 2,3,4	Computer/Form
	BPI	2,3,4	Computer/Form
Fatigue	NRS, BORG CR10	1,2,3,4	Computer/Form
QST	PPT (C,L, Ant Tib)	2,3,4	Algometer, Form, Marker, Alcohol swab
	CPM	2,3,4	Bucket, thermometer, Water, Ice, Towel, Form
Function	6MWT	2,3,4	Timer, Form, Distance Measurement, Pulse Oximeter, BP Cuff, Sphygmometer
	FTSTS	2,3,4	Timer, Form, Chair with arms
	Functional Reach	2, 3,4	Yardstick, Form
	Accelerometry	1,3,4	Actigraph, home tracking, initialization & instruction sheet
TENS	TENS Trial	1	TENS, Electrodes, Batteries, Lead
	TENS Treatment at Visit	2,3,4	TENS, Lead wires, Electrodes, Batteries, Participant Handbook
Handbooks	Participant Assessor	1,2,3,4	Handbook

Data Analysis Plan

Aim	Visit (V)	Measures	Statistical Plan
General Considerations	V1 V2 V3 V4	All outcome measures: Pain NRS rest and movement, Fatigue NRS rest and movement, BPI, PPT, 6MWT, FTSTS, FR, CPM, Accelerometry FIQR, SF-36, TSK, GIC, PROMIS, MAF,	
 • Descriptive Statistics • n, mean, standard deviation, standard error, median, first and third quartiles, minimum, maximum • Outcomes summarized by visit • Changes from visit to baseline; shift tables may be used to investigate shifts from visit 1 to visit 3 • • If variables not normally distributed, non-parametric tests will be used

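### Session 4 has no adverse-event screen after its testing, so non-pain events from the final on-site session are not systematically asked about

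*Combined protocol and SAP*

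**What the plan says.** The Safety Measures row of the Study Synopsis lists "Adverse Event analysis" among the safety measures, without further detail. The collection points appear in the table headed "Order of Testing FAST June 2014", which has one column per session.

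- **Sessions 2 and 3:** each has an "Adverse Event Screen" before testing and an entry AES near the end, after the last CPM test.
- **Session 1:** two screens, with the blood draw listed after the second.
- **Session 4:** one screen, before testing. The column ends with CPM, the global impression of change (with TENS off beside it) and two entries marked only as surveys.

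Two other provisions bear on the point. The Safety Measures row, under its item on increased pain with testing, says: "Participants who experience an increase in testing will be contacted the day after testing about the status of the increase in pain (Added 12/2014". The Study Summary row says: "Subjects will receive a phone call weekly from the study coordinator regarding progress".

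**The concern.** An adverse-event question put before a procedure cannot collect what the procedure causes. At Visits 2 and 3 a closing screen follows the testing. At Visit 4 none is listed, and no later visit exists at which the question could be put.

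The testing is not trivial for this population. Session 4 repeats the six-minute walk, sit-to-stand, functional reach and pressure-pain tests around a TENS session and ends with CPM, for which the equipment list in Table 3 gives "Bucket, thermometer, Water, Ice, Towel, Form". The plan itself anticipates skin problems, since severe adhesive allergy and nickel allergy are exclusion criteria. At Session 4 TENS goes off only after the sole screen.

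At stake is the completeness of the safety data from the last on-site session, when every woman still in the study is on active TENS. The efficacy analysis is not involved.

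**Working it through.** No arithmetic beyond counting applies. The check is a row-by-row reading of the order-of-testing table against the other safety provisions.

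**Step 1. Screens per session.**

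| Session | Opening screen | Closing screen | Listed after the last screen |
|---|---|---|---|
| 1 | 1 | 1 | Blood draw |
| 2 | 1 | 1 (AES) | Recording and clearing data |
| 3 | 1 | 1 (AES) | Recording and clearing data |
| 4 | 1 | 0 | All testing |

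**Step 2. What follows the Session 4 screen.** The screen is entry 4 of 20, so 20 − 4 = 16 entries come after it. They include two six-minute walks, two sit-to-stand tests, two functional reach tests, two pressure-pain runs, one TENS session and one CPM test.

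**Step 3. Could text extraction have lost an entry?** This is unlikely. The Session 4 cells beside the last rows of Session 3 are blank, which fits a column that ended earlier.

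**Step 4. Does anything else listed put the question?**

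- *A later visit:* none. The Study Design row and the Schedule of Visits and Evaluations both give four visits.
- *The next-day contact:* it is not limited by visit, so it applies after Visit 4. It is triggered by an increase in pain and asks about that pain.
- *The weekly calls:* their subject is progress. Adverse events are not named, and no call after Visit 4 is stated.
- *Ratings during testing:* the repeat walk is listed as "6MWT (NRS Mvmt Pain, Fatigue, BORG", and the repeat sit-to-stand test also carries pain and fatigue ratings. These do not ask about skin, dizziness or a fall.
- *The two survey entries:* their content is not defined, so they cannot be counted on to ask about adverse events.

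**Step 5. What is left.** Increased pain has a stated follow-up after Session 4. Non-pain events from that session have no listed question.

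**Step 6. Session 1.** The blood draw comes after the second screen, but Session 2 opens with a screen before its testing. An event from the blood draw is therefore asked about late, at Visit 2.

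**The case against.** The strongest reply is that a missing prompt does not mean events go unrecorded. The assessor is present throughout, so a fall or faint during testing would be seen. Session 4 includes a five-minute TENS check. The walk equipment at Visits 2 to 4 includes a pulse oximeter and a blood pressure cuff. The Safety Measures row also lists physical exam, vital signs, and clinical signs and symptoms, with no visit attached. The table is a June 2014 workflow list, and the pain contact was added in December 2014, so the table is not the whole safety plan. AES is never spelled out.

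Much of this stands, and it rules out several stronger readings that a reader might infer:

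- *Events from Session 4 are never asked about.* The next-day contact covers increased pain at any visit, and staff observation and spontaneous report remain.
- *The open active-TENS month will look safer than it is.* The opening screen at Session 4 comes after that month and covers home use. Only the on-site procedures fall after it.
- *Event counts by session will not be comparable.* No per-session comparison is planned.
- *The share of all walks or cold-water tests performed at Session 4 measures the loss.* It counts tests, not events. A debriefing note in Session 3 may also mean that some women on active TENS skip the second test block there, so the number of tests per woman is not fixed.

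The reply does not supply a question about non-pain events after the Session 4 testing. Observation catches what happens in view. It is less reliable for a mild skin reaction or for dizziness that the woman does not mention.

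**Conclusion.** The point holds in a narrow form. Session 4 lacks the closing adverse-event screen that Sessions 2 and 3 have. Non-pain events from its on-site TENS session, walks and ice-water test are therefore not systematically solicited.

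The reach is one visit's on-site procedures, for every woman who attends Visit 4; the planned final sample is 264. The documents give no event rates, so no number of missed events can be stated. The randomized comparison is untouched, because Sessions 2 and 3 have both screens.

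The conclusion assumes that AES means the adverse-event screen, that the order of testing is followed as printed, and that neither survey entry at the end of Session 4 is an adverse-event form. If a survey does contain that question, the gap closes and the table need only say so.

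The Session 1 order is a delayed question and a matter of tidiness. The Session 4 change should be made: it improves safety collection at almost no cost.

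**What to change.** Add the existing closing AES to the Session 4 column, after CPM and after TENS is off, as the last procedure before the woman leaves. Spell out AES in the table. State that events reported on this form are included in the adverse-event analysis with the other on-site events.

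Optionally, move the closing screen in Session 1 to after the blood draw.

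The cost is one short existing form per woman at Visit 4 and, if the option is taken, a swap of two lines at Visit 1. No new staff or instrument is needed, and no treatment or endpoint changes.

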Exclusion Criteria	
 • Current or history of cardiovascular, pulmonary, neurological, endocrine, or renal disease that would preclude the involvement in the study. • TENS use in the last 5 years • Pacemaker • Uncontrolled blood pressure or diabetes • Neuropathic pain condition • Systemic autoimmune disorder (Lupus, PMR, RA, Psoriatic arthritis) • Spinal fusion – cervical or lumbar • Metal implants in the spine • Severe skin allergy to adhesive • Allergy to nickel • Pain less than 4 • Pregnancy • Epilepsy • Change in or new drug or treatment program within the last month or in the next 2months, i.e. must have a stable treatment plan • Unstable medical or psychiatric condition which in the opinion of the investigator could compromise the subject’s welfare or confound the study results
Planned Sample Size	Final sample size of 264 subjects divided into 88 subjects per group. We will recruit 316 subjects based on a 20% projected attrition.
Randomization	Patients will be randomly allocated on the second visit after a re-assessment of eligibility. We will use a permuted block schedule, stratified by site. The randomization schedule will be implemented using SAS v9.2 PROC PLAN, creating blocks of size 6 for each of the strata factors.
Study Device Dosage and Administration	
FDA Summary of Empi Select TENS Unit: TENS is a non-pharmacological agent which delivers electrical stimulation by a battery operated device via electrodes placed on the skin. TENS is considered to be a safe, inexpensive and non-invasive modality used to treat a variety of acute and chronic pain conditions.
 
510(k) Summary for 300 PV Complete Electrotherapy Systems 1. Manufacturer Empi [name]

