Criteria for Evaluation	
Primary Efficacy Endpoint:
 
 • Pain with movement (NRS) during 6MWT 
Secondary Efficacy Endpoints:
 
 • Health History/Demographics • Vital Signs • Confirmation of ACR 1990 Criteria for FM/Tender Point Exam • 2010 ACR Criteria • NRS Rest Pain, Rest Fatigue, Movement Pain, Movement Fatigue • BPI • PROMIS • FIQR • SF-36 • MAF • TSK • IPAQ • PSQI • PSEQ • PCS • Global Impression of Change • Accelerometry • 6MWT • STS • FR • PPT • CPM • TENS • Blinding
Statistical Methods	
 • Continuous variables will be summarized with descriptive statistics (n, mean, standard deviation, standard error, median, first and third quartiles, and minimum and maximum). • Categorical variables will be described with counts and percentages. The endpoints (VAS, BPI, PPT, CPM, and 6MWT, STS, FR and accelerometry measures) will be treated as continuous variables as well as scores from questionnaires (FIQR, SF-36, MAF, and TSK, PROMIS). • Changes from initial measurement to one month after randomization will be calculated for each of these endpoints. Changes in outcomes and percent changes in outcomes will be treated as continuous variables and will be summarized with descriptive statistics. Outcomes will be summarized by visit, as change from initial measurement, and percent

	
change from initial measurement. Continuous endpoints may also be categorized into discrete variables when appropriate. Shift tables may be utilized to investigate shifts in outcome categories from baseline to one month after randomization. SAS v9.2 or higher will be used for all analyses and a significance level of 0.05 will be used for all statistical tests. In the case that endpoints are found to be non-normal, appropriate transformations will be employed and non-parametric tests may be used

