
Statistical Methods Aim #1- #4
	
Aim #1: The primary endpoint of Aim #1 is the change (visit 3- visit 2) in pain scores during movement. In order to evaluate the effectiveness of long-term use of TENS (Aim 1), the primary analysis will be the comparison of change in pain (with movement for those randomized to either active TENS, placebo TENS, or standard of care). The comparison of the change (visit 3 – visit 2) in pain for the three groups will be made using linear mixed model analysis for repeated measures with treatment group, time (visit2 and visit3), and treatment group*time interaction as the fixed effects. The test for the treatment group*time interaction effect corresponds to the test comparing mean change among the groups. Post-hoc pairwise comparison of mean change between groups will performed by test of mean contrasts estimated from the fitted linear mixed model with p-values adjusted using Bonferonni’s method to account for the number of tests performed (i.e. 3 tests for all pairwise comparisons). It is expected that the randomization will lessen the need for covariate-adjusted analyses. However, in the event that adjusted analyses are necessary, a secondary comparison of the change in endpoints for the three groups will be made by expanding the linear mixed model to include covariates. Potential confounders include age, race, ethnicity, educational attainment, marital status, TENS dose/intensity, change in opioid status, medication intake and use of rescue medications.
 
While every effort will be made to follow-up with patients, preliminary data suggests that approximately 10% of the patients will not return for follow-up. The ITT analysis will be performed using all available data for all randomized participants. In the presence of missing data, under the assumption of missing at random (MAR), linear mixed model analysis which can handle incompletely observed subjects and uses a likelihood estimation method will provide correct likelihoods and lead to valid estimates (ref1). However, since the data under analysis cannot distinguish if data is MAR or it is missing not at random (MNAR), sensitivity analysis will also be performed using pattern mixture models. Multiple imputations will be used for sensitivity analysis by imputing from a non-random pattern mixture model (ref2).
 
Furthermore, based on previous work, it is expected that approximately 5% of subjects randomized to active TENS may not receive a full dose of active TENS because they did not achieve the adequate intensity dose. In the primary ITT analysis, these patients will be included as randomized. However, as an additional analysis a modified ITT (mITT) analysis will be conducted. This analysis will utilize an ITT principle in terms of randomization but will be limited to those who achieved at least one adequate intensity dose.
 
(ref1) Molenberghs G. and Kenward MG (2007) Missing Data in Clinical Studies. John Wiley & Sons Ltd, West Sussex, England.

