Aim #1	V3-V2	Pain NRS with movement (6MWT and FTSTS) for the treatment groups: active TENS, placebo TENS or standard care	
 • Linear mixed model analysis (LMM) for repeated measures with treatment group, time (V3-V2) and treatment group*time interaction as fixed effects. • Post-hoc pair wise comparison of mean change between all three treatment groups • p-values adjusted using Bonferroni method to account for the number of tests • Potential confounders include BMI, age, race, ethnicity, educational attainment, marital status, TENS dose/intensity, change in opioid status, medication intake, rescue medications; If there are differences between potential confounders, we will include covariates
Aim #1 Intention to Treat (ITT)	V3-V2	Pain NRS with movement (6MWT and FTSTS) for the treatment groups: active TENS, placebo TENS or standard care	
 • Intention to treat (ITT) analyses using all available data for all randomized participants will be used • If there are missing data, missing at random (MAR) LMM will be used. Sensitivity analysis will be performed using pattern mixture models since data cannot be determined if it is MAR or missing not at random (MNAR). Multiple imputation will be used for sensitivity analysis by imputing from a non-random pattern mixture model • Modified ITT (mITT) will be conducted to account for subjects who did not achieve adequate dose (based on previous work, 5% of subjects randomized to active TENS

			are expected to not achieve adequate dose). This will be limited to those who achieved at least one adequate intensity dose ^{73, 74} .
Aim #2	V3-V2	Primary: Fear of movement scores. Secondary: changes in function, fatigue, resting pain, use of rescue medications, accelerometry and quality of life questionnaires.	
 • Comparison between the randomized groups will be performed as described in Aim #1. • Additional analysis using the change in fatigue, fear of movement, function, resting pain measures and quality of life as dependent variable in linear regression models, associations between these outcomes and changes in pain values will be investigated.

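### Covariate adjustment for Aim #1 hangs on an undefined imbalance trigger, and the Data Analysis Plan does not repeat the synopsis's statement that the adjusted model is secondary

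*Combined protocol and SAP*

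**What the plan says.** **Study Synopsis, Statistical Methods Aim #1-#4.** The primary analysis is a linear mixed model with "treatment group, time (visit2 and visit3), and treatment group*time interaction as the fixed effects". Pairwise contrasts are Bonferroni-adjusted for "3 tests for all pairwise comparisons". On covariates, the synopsis expects randomisation to reduce the need for adjustment, and then says that "in the event that adjusted analyses are necessary, a secondary comparison of the change in endpoints for the three groups will be made" by adding covariates to the mixed model. It does not say what would make adjustment necessary.

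**Data Analysis Plan, Aim #1 row.** The first bullet gives the same covariate-free model. A later bullet reads "Potential confounders include BMI, age, race, ethnicity, educational attainment, marital status, TENS dose/intensity, change in opioid status, medication intake, rescue medications", followed by "If there are differences between potential confounders, we will include covariates". It names no comparison, test, threshold or timing, and does not say whether the adjusted model replaces or accompanies the unadjusted one. BMI is in this list but not in the synopsis list.

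**Aim #2.** Both the synopsis and the Data Analysis Plan send the Aim #2 group comparisons back to the Aim #1 method, so the rule carries over to fear of movement and the other Aim #2 outcomes.

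**The concern.** In a randomised trial, a difference between arms on a baseline variable arises by chance. Its size says nothing about whether the variable predicts change in movement pain. A rule based on imbalance can therefore leave out a strong predictor that happens to be balanced and bring in an irrelevant variable that happens not to be.

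The rule also means that whether an adjusted result exists, and what it adjusts for, is decided after the arms have been compared. Because the trigger is undefined, two analysts could follow the text faithfully and produce different adjusted results.

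The list adds a further problem. Four of its entries (TENS dose or intensity, opioid change, medication intake, rescue medication) are or can be measured after randomisation. TENS dose must differ between arms, since one arm has no TENS. Read literally, the rule then calls for adjustment on a consequence of allocation, which could bias the treatment effect or remove part of it.

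**Working it through.** **Inputs from the documents.** "Final sample size of 264 subjects divided into 88 subjects per group" (3 × 88 = 264), and "a significance level of 0.05 will be used for all statistical tests", taken here as two-sided. Bonferroni over three contrasts gives 0.05/3 = 0.0167 each. The documents give no effect size, SD, power, covariate R-squared or balance-test threshold, and no figure for the gain from adjustment. There is therefore no stated figure to reproduce.

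**Assumptions.** One normally distributed baseline covariate, complete data, R-squared for change in pain from 0.02 to 0.30, and a balance test at 0.05, 0.10 or 0.20.

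**1. Share of the gain lost under the trigger.** Adjustment removes the part of the variance that comes from chance imbalance. Under the trigger, it does so only when the balance test rejects at level a.
- Three-arm test (2 df): share lost = P(χ² on 4 df < q), where q = −2 ln a. This equals 1 − a(1 − ln a). At a = 0.05: 1 − 0.05 × (1 + 2.996) = 0.80.
- Two-arm test: share lost = (1 − a) − 2cφ(c), where c is the two-sided critical value. At a = 0.05: 0.95 − 2 × 1.96 × 0.0584 = 0.72.

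| Balance test level | Lost, three-arm test | Lost, two-arm test |
|---|---|---|
| 0.05 | 80% | 72% |
| 0.10 | 67% | 56% |
| 0.20 | 48% | 35% |

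Simulation of the three-arm case at 88 per arm (20,000 trials per setting, R-squared 0.10 and 0.30) kept 19–24% of the gain at 0.05 and 48–54% at 0.20, in line with the formula.

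**2. Size of the gain.** Suppose unadjusted power is 80% for one contrast at 0.0167. The detectable difference is then (2.394 + 0.842) × √(2/88) = 0.488 SD. Always adjusting scales the SD by √(1 − R²):

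| R-squared | Power, always adjusted |
|---|---|
| 0.02 | 80.9% |
| 0.05 | 82.3% |
| 0.10 | 84.5% |
| 0.20 | 88.9% |
| 0.30 | 93.0% |

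Simulated power (10,000 trials, trigger 0.05) for unadjusted, triggered and always adjusted was 80.4%, 80.7% and 84.4% at R-squared 0.10, and 80.0%, 81.2% and 92.9% at R-squared 0.30.

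**3. Type I error.** Under the imbalance rule, simulated type I error for one contrast was 0.012 to 0.015 against a nominal 0.0167.

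**4. Form of adjustment.** With two visits and complete data, the group-by-time contrast is a difference in mean within-person change. A baseline covariate entered only as a main effect cancels out of that change. In one simulated data set at 88 per arm, the estimate was −0.906 (SE 0.240) both without the covariate and with it as a main effect. Adding covariate-by-time gave −0.967 (SE 0.226). The gains in step 2 therefore need covariate-by-time terms or an ANCOVA form.

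**5. How often chance fires the trigger.** For the six baseline items (BMI, age, race, ethnicity, education, marital status), assumed independent, the chance that at least one fires is 1 − 0.95⁶ = 26.5% at 0.05 and 1 − 0.80⁶ = 73.8% at 0.20. For TENS dose or intensity no chance calculation applies, because the difference is built into the design.

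**The case against.** The strongest reply is that the primary model is already fixed. The synopsis names a covariate-free mixed model as primary and places adjustment second. The first bullet of the Aim #1 row repeats that model, and the covariate bullet is naturally read as a shortened form of the synopsis text. An unadjusted primary analysis of a randomised trial is valid. This reply largely stands. A reader of the Data Analysis Plan alone might infer that the primary model is itself chosen after looking at the data, and the synopsis does not support that.

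A reader might also infer that false-positive risk rises. Step 3 shows that it does not under the rule as such. Inflation would require someone to report the better of two results against the stated hierarchy.

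A third reply is that little precision is at stake. The plan speaks only of expanding the model with covariates, and main effects alone change almost nothing. Prognostic strength is also unknown, and demographic variables may be weak predictors. This stands as a limit on size, so a flat claim that most of the gain from adjustment is lost goes beyond the documents.

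None of these replies defines the trigger, restores the missing statement that the adjusted model is secondary, or explains how a variable fixed by arm can sit under an imbalance rule.

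**Conclusion.** The point holds as a fault in a stated rule, not as a threat to the validity of the primary test. The adjusted analysis, and its counterpart under Aim #2, depends on undefined and data-dependent conditions. The two sections must be reconciled on its status. The literal rule also reaches a variable that differs by design, and adjusting for that variable could bias the comparison.

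The loss of precision is conditional. For one covariate and a three-arm balance test, it is about 80% of the available gain at 0.05, 67% at 0.10 and 48% at 0.20. The available gain is about 1 to 2 power points at R-squared 0.02–0.05 and 13 points (80% to 93%) at 0.30. These figures assume 80% unadjusted power, two-sided tests at 0.0167, 88 per arm, complete data, and adjustment in a form that acts on change. R-squared and the trigger level are not in the documents. The change should be made, but the trial does not depend on it.

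**What to change.** 1. In the Data Analysis Plan, Aim #1 row, delete the sentence that adds covariates when differences are seen. In the synopsis, delete the clause that makes the adjusted analysis depend on its being necessary.
2. State in both places that the primary model is fixed whatever the observed balance, and that the adjusted analysis is secondary.
3. Always run one adjusted analysis with a short set of pre-randomisation covariates, named before unblinding for their expected relation to change in movement pain. Site, as the stratification factor, is a natural candidate.
4. Specify the form: covariate-by-time terms in the mixed model, or ANCOVA on visit 3 pain with a visit 2 pain value recorded before any allocated treatment.
5. Do not use balance tests to select covariates, and take post-randomisation variables off the list.
6. Say that the same rule applies to the Aim #2 group comparisons.

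The cost is a few sentences of analysis text, with no change to conduct or sample size. Covariates can no longer be chosen after seeing the data, and the adjusted model uses a few degrees of freedom.
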